
## SCHEMATIC OF STUDY DESIGN

## SCHEDULE OF STUDY VISITS AND PROCEDURES

1  
2  
3

	Screening Visit	CIQ 1.5/ Humalog Training Visit	CIQ 1.5/ Lyumjev Training Visit	Control-IQ Use								
				3d	1w	2w	3w	6w	9w	13w	UV	
		Lead-In	Start Main Trial ~16 days after start of Lead-In									
Visit (V) or Contact (C)	V	V	V	C	C	C	C	V	C	V	V/C	
Informed Consent/Assent	X											
Eligibility Assessment	X											
Medical history/ physical exam a	X			X	X	X	X	X	X	X	X	
Height, weight, blood pressure and pulse	X		X									
HbA1c (POC or local lab)	X											
ECG b	X											
Questionnaires/Surveys (PRO Assessments) c	X									X		
Pregnancy test (females of child-bearing potential)	X		X									
Assessment of Device Use	X		X									
Study system training		X	X									
HbA1c (Central Lab)			X							X		
AE Assessment		X	X	X	X	X	X	X	X	X	X	
Upload device data from home				X	X	X	X		X		X	
Download device data at clinic visit	X	X	X					X		X	X	

4 a A qualified medical professional must perform a medical assessment at each office visit. During each office visit, the skin  
5 surrounding the infusion sites should be assessed as part of a focused physical exam. This also applies for all phone visits  
6 converted to an office visit, as well as unscheduled visits that occur in the office.

7 b ECG performed at screening for participants age >50 years, duration of diabetes > 20 years, or history of coronary artery disease

8 c TRIM-D, Trim-DD (Diabetes Device), ITSQ (Insulin Treatment Satisfaction Questionnaire)

9  
10  
11

12

13

14

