## 303 **2.4 Screen Failures**

304 Individuals who do not initially meet study eligibility requirements may be rescreened one more time at a  
305 later date per investigator discretion.

306 **2.5 Lead-in Period**

307 All participants will complete the Lead-in Period as an outpatient for approximately 16 days. The Lead-in  
308 Period may begin the same day the screening visit is completed or within 4 weeks after informed consent  
309 is signed. The lead-in period will last at least 16 days and no more than 21 days.

310 At the initiation of the Lead-in Period (CIQ 1.5/ Humalog Training Visit), participants will switch from  
311 their current Control-IQ system to the study pump (Control-IQ 1.5 technology), study sensor, and study-  
312 provided Humalog (insulin lispro injection). Training will be provided by qualified study staff on the  
313 study pump, the study CGM sensor, the study glucose meter, and the study ketone meter. The study  
314 investigator may adjust insulin delivery profile settings as indicated.

315 During the lead-in period, each participant will perform one meal and exercise challenge to determine a  
316 baseline using Humalog and Control-IQ 1.5. Those day and overnight periods will be analyzed separately.  
317 Procedures are described in section 5.1. A minimum of 48 hours will occur between all challenges for  
318 each participant.

319 After 16 days (and up to 21 days), the participant will have a visit. System use will be assessed and to  
320 proceed to the Treatment Period, it is necessary that a participant used the Control-IQ system, with at  
321 least 85% of system use (active closed loop) reported over the time of the lead-in period (ie, minimum of  
322 85% of 14 days).

323 The lead-in period data collection may be repeated if this threshold is not met.

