## 584           **5.2 Laboratory Testing**

### 585           **5.2.1 HbA1c**

586           HbA1c measurement will be performed locally at the Screening visit.

587           An additional blood sample will be obtained (venipuncture or fingerstick) and sent to central lab at the  
588           CIQ 1.5/Lyumijev Training visit and at the 13-week visit.

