996 CGM metrics will be computed for (1) 4 weeks pre-study (personal CGM), (2) Lead-in Period, and  
997 (3) Treatment Period. CGM metrics will be computed over 24 hours, during daytime (6am-11:59pm),  
998 during nighttime (12mn-5:59am), and during scheduled exercise and meal challenges.

999 The main statistical comparison will be made between the Treatment Period and the Lead-in Period. The  
1000 lead-in period time for analysis will exclude the day and night of the baseline exercise and meal  
1001 challenges. Additionally the Treatment Period will be compared with the pre-study CGM data.

1002 Linear mixed models will be used to test the change from pre-Treatment Period to Treatment Period.  
1003 Missing data will be handled by the method of direct likelihood, which assumes outcomes are missing at  
1004 random and estimates follow-up values via maximum likelihood. Sensitivity analyses will be  
1005 performed to assess the robustness of the results under different missing data assumptions.

1006 **8.6.3 Analysis of HbA1c and PRO Measures**

1007 Linear mixed models will be used to test the change in HbA1c and PRO scores from baseline to  
1008 13 weeks. Missing data will be handled by the method of direct likelihood, which assumes outcomes are  
1009 missing at random and estimates follow-up values via maximum likelihood.

1010 **8.7 Intervention Adherence**

1011 The following tabulations will be performed:

- 1012 • Sensor use—percent time of use
- 1013 • Closed loop system use—percent time of use
- 1014 • % time in different operational modes

1015 **8.8 Protocol Adherence and Retention**

1016 The following tabulations and analyses will be performed to assess protocol adherence for the study:

- 1017 • Number of protocol deviations
- 1018 • Flow chart accounting for all enrolled participants
- 1019 • Number of and reasons for unscheduled visits and phone calls
- 1020 • Number of participants who were enrolled but did not enter the Treatment Period and reasons
- 1021 • Number of participants who stopped treatment and reasons

1022 **8.9 Baseline Descriptive Statistics**

1023 Baseline demographic and clinical characteristics of the cohort of participants who initiate the Treatment  
1024 Period will be summarized in a table using summary statistics appropriate to the distribution of each  
1025 variable. Descriptive statistics will be displayed by treatment group for the following:

- 1026 • Age
- 1027 • Sex
- 1028 • Race/Ethnicity

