$$\frac{\text{Raw Score} - \text{Lowest Possible Raw Score}}{\text{Range of Possible Raw Scores}} \times 100$$

253 If any items are unanswered the total score and subscale pertaining to that item will not be  
254 calculated.

255 **6.5.2 ITSQ**

256 Items on the ITSQ are scored on a 7-point Likert scale. The raw total score and subscale scores  
257 are computed by calculating the mean across all non-missing item scores. Scores are then  
258 transformed to a 0 to 100 scale by using the following formula:

259 
$$\frac{7 - \text{Raw Score}}{6} \times 100$$

260 At least 75% of items must be non-missing to calculate scores.

261 **7 Analyses Cohorts**

262 All participants who initiate the treatment and provide at least 24 hours of CGM data will be  
263 included in the analyses.

264 **7.1 Analysis Windows**

265 The central lab HbA1c measured at the end of the lead-in period must be collected within 21  
266 days before to 7 days after the Lyumjev training visit, and the HbA1c measured at the end of the

267 treatment period must be collected within 42 days before to 30 days after the 13-week target date  
268 (91 days after the Lyumjev training visit). HbA1c measurements collected outside the analysis  
269 windows will be treated as missing.

270 The PRO outcomes at screening must be collected prior to the Lyumjev training visit, and PRO  
271 outcomes at 13 weeks must be collected within 42 days before to 30 days after the 13-week  
272 target date (91 days after the Lyumjev training visit). PRO outcomes collected outside the  
273 analysis windows will be treated as missing.

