### 289 **8.2 Secondary Safety Analyses**

290 The total number of any type of adverse event, number and proportion of participants who  
291 experienced at least one adverse event during the treatment period and the rate of adverse events  
292 per 100 person years will be tabulated. For the CGM metrics listed in Section 5.2, summary  
293 statistics for each metric will be reported during the pre-study, lead-in, and treatment periods.

294 The main analyses will compare metrics from the lead-in period to the treatment period, and  
295 additional analyses will compare the pre-study period to the treatment period. Linear mixed  
296 models including study visit as a fixed effect and clinical site as a random effect will be used to  
297 estimate the mean change from the lead-in period to the treatment period. Similar models will be  
298 used to estimate the change from the pre-study period to the treatment period. A point estimate,  
299 two-sided 95% confidence interval and two-sided p-value will be reported from the models. If  
300 residuals are highly skewed, then a transformation or non-parametric method will be used.  
301 Summary statistics for all secondary safety endpoints will be tabulated separately for pediatric  
302 and adult participants, and by more detailed age groups (6-13, 14-17, 18-25, 26-49,  $\geq 50$ ).

303 **8.3 Exploratory Analyses**

304 Linear mixed models including study visit as a fixed effect and clinical site as a random effect  
305 will test the change from the lead-in period to the treatment period for all exploratory CGM,  
306 insulin, and HbA1c endpoints. If a central lab HbA1c is not available at baseline the screening  
307 HbA1c will be used. Similar models will test the change from screening to the end of the  
308 treatment period for patient reported endpoints. A point estimate, two-sided 95% confidence  
309 interval and two-sided p-value will be reported from the models. If residuals are highly skewed,  
310 then a transformation or non-parametric method will be used. For CGM metrics, a similar model  
311 will be used to test differences between the pre-study period and the treatment period. All  
312 analyses will be replicated for daytime, nighttime, and postprandial CGM metrics. A sensitivity  
313 analyses will compare all 24 hour CGM metrics between the lead-in and treatment periods  
314 restricting to complete cases. Summary statistics for all exploratory endpoints will be tabulated  

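### SAP 8.3 fills a missing central-lab baseline HbA1c with the local screening value, so for those participants the tested change also contains any local-to-central difference and any lead-in change (minor; exploratory endpoint)

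*SAP*

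**What the plan says.** **The contrast.** The mixed models of SAP 8.3 "will test the change from the lead-in period to the treatment period for all exploratory CGM", insulin and HbA1c endpoints. SAP 13 likewise places HbA1c in the lead-in versus treatment group for multiplicity.

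**The intended measurements.** Protocol 5.2.1: "An additional blood sample will be obtained (venipuncture or fingerstick) and sent to central lab at the" Lyumjev training visit and at 13 weeks. Both ends of the contrast are thus central-lab.

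**The substitute.** SAP 8.3: "If a central lab HbA1c is not available at baseline the screening" value takes its place. SAP 7.1 treats a central-lab baseline drawn more than 21 days before or 7 days after the Lyumjev training visit as missing, so such a value would presumably also be replaced. SAP 7.1 gives no window for the screening substitute. The rule entered in SAP version 3.0, during enrollment.

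**What the screening value is.** Protocol 5.2.1: "HbA1c measurement will be performed locally at the Screening visit". The visit schedule lists it as "HbA1c (POC or local lab"). It precedes the lead-in, at whose start (Protocol 2.5) participants switch from "their current Control-IQ system to the study pump (Control-IQ 1.5 technology), study sensor, and study"-provided Humalog. Pump settings may also be adjusted then.

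**The protocol's method.** Protocol 8.6.3, on HbA1c and PROs: "Missing data will be handled by the method of direct likelihood, which assumes outcomes are" missing at random and that follow-up values are estimated by maximum likelihood. It gives no substitution rule.

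**The concern.** The lead-in puts every participant on the same pump version, sensor and insulin before Lyumjev starts, and the central laboratory puts both HbA1c values on one measurement footing. A screening value entered as the baseline has neither property. For that participant the computed change runs from the pre-study system, measured locally, to Lyumjev, measured centrally.

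Any systematic difference between local and central measurement, and any shift over the lead-in, then counts as change on Lyumjev. The direction cannot be told from the documents. Nothing planned would reveal it: the complete-case sensitivity analysis in SAP 8.3 covers only 24-hour CGM metrics, and the SAP does not ask for the number of substituted baselines to be reported.

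**Working it through.** The documents give no HbA1c effect, SD or missing-baseline rate, and both state that the 160 completers were not chosen on statistical principles. There is no plan figure to reproduce. The timing comes from the documents. The sizes rest on assumptions, marked as such.

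**1. Age of the substitute.** Protocol 2.5 lets the lead-in begin on the day screening is completed or within 4 weeks after consent, and it lasts 16 to 21 days. Taking the screening sample as drawn at about the time of consent:
- shortest gap to the Lyumjev training visit: 0 + 16 = 16 days
- longest, with a single lead-in: 28 + 21 = 49 days

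A repeated lead-in lengthens this. The short end lies inside the 21 days that SAP 7.1 allows a central-lab baseline; the long end does not.

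**2. Bias.** Let f be the share of participants with a substituted baseline and d the mean difference between the screening value and the central-lab value it replaces. The mean change is then shifted by

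bias = f × d

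Assumed: f = 2% to 20%, d = 0.1 to 0.3 HbA1c points, SD of change 0.4 to 0.6, N = 160. The standard error is SD/√160, which is 0.4/12.65 = 0.032 to 0.6/12.65 = 0.047. If the true change is zero, the two-sided 5% test rejects with probability Φ(−1.96 + bias/SE) + Φ(−1.96 − bias/SE).

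| f | Participants of 160 | Bias, d = 0.1 to 0.3 | Actual two-sided error |
|---|---|---|---|
| 2% | 3 | 0.002 to 0.006 | 5.0% to 5.4% |
| 5% | 8 | 0.005 to 0.015 | 5.1% to 7.6% |
| 10% | 16 | 0.010 to 0.030 | 5.5% to 15.8% |
| 20% | 32 | 0.020 to 0.060 | 7.1% to 47.5% |

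The upper error at 10% comes from d = 0.3 and SD = 0.4: bias/SE = 0.030/0.0316 = 0.95. The 20% row only shows what frequent substitution would do; nothing in the documents suggests it.

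**3. Price of not substituting.** Assumed: between-person SD 0.8; within-person SD 0.25 at screening, 0.20 at end of lead-in and 0.35 at 13 weeks; 16 of 160 baselines missing at random.
- Substitution: variance of change = 0.9 × (0.20² + 0.35²) + 0.1 × (0.25² + 0.35²) = 0.9 × 0.1625 + 0.1 × 0.185 = 0.16475. SE = √(0.16475/160) = 0.0321. Any offset adds a little to this.
- Three visit levels fitted by likelihood, screening mean left free: SE = 0.0327 (generalised least squares with the same variances).
- Two visit levels, baseline simply left missing: SE = 0.0334.

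The three-visit model costs 0.0327/0.0321 = 1.02, about 2% in standard error, and the f × d term is zero under missing at random. Leaving the baseline missing costs 0.0334/0.0321 = 1.04, about 4%.

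**The case against.** Much can be said for the SAP.

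- **Protocol conflict.** A reader might infer that the substitution contradicts the protocol and so disproves the consistency statement in SAP 1. The text does not go that far. Protocol 8.6.3 speaks of estimating follow-up values, never defines the HbA1c baseline and does not forbid a second observed value. Elsewhere screening HbA1c already serves as baseline: the enrollment goal of 7.5% or more is worded as baseline in Protocol 2.1 and as screening in SAP 4, and SAP 9 tabulates the screening value. What stands is that substitution is no part of the direct-likelihood approach the protocol names, and that SAP 8.3 and 7.1 do place the tested baseline at the end of the lead-in.
- **Standard error.** One might infer that precision is overstated, as with single imputation. It is not, on that account: screening HbA1c is an observed measurement, and its scatter enters the residual variance. The problem is bias alone.
- **Timing and insulin.** Seven weeks is the single-lead-in maximum, not the typical gap. All participants already used Control-IQ, and some continued Humalog, so the lead-in shift may be small. The local-to-central difference remains. The assays are not named, so a change of assay is not established, only a change from point-of-care or local lab to central lab.
- **Size.** Share, offset and SDs are all assumed. The sample is due at a visit every participant must attend to start Lyumjev, so frequent missingness is not to be expected. Stating the bias as a percentage of the treatment effect would need an effect size that the documents do not give.
- **Importance.** HbA1c change is exploratory, there is no formal efficacy hypothesis, and the version history discloses the rule.

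**Conclusion.** The point holds and is minor. For any participant with a substituted baseline, the change tested in SAP 8.3 mixes the intended contrast with a local-to-central difference and the lead-in change. Under assumed offsets of 0.1 to 0.3 points the bias is at most 0.006 at 2% substituted, 0.015 at 5% and 0.03 at 10%. The last is still slightly below one standard error at the smaller assumed SD. It is probably small unless substitution was common, which the documents leave unknown. They do not support calling it a breach of the protocol or a fault in the standard error. It merits correction because the cure is specific, uses data already collected and costs little precision.

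**What to change.** In SAP 8.3, drop the substitution from the main HbA1c test. Fit the linear mixed model by direct likelihood with three visit levels: screening (local), end of lead-in (central) and 13 weeks (central). State the within-participant covariance, since SAP 8.3 names only clinical site as a random effect. Report the 13-week minus end-of-lead-in contrast. The screening value then still informs a missing baseline through its correlation, while its mean is free to differ.

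Keep the substitution as a sensitivity analysis and report how many baselines it affects, separating absent samples from those set to missing under SAP 7.1.

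Cost: SAP wording and one extra visit level, with no new data. The interval is slightly wider, with a standard error about 2% larger at 10% missing under the SDs assumed above.

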## 344 **9 Baseline Descriptive Statistics**

345 At the initiation of the treatment period summary statistics appropriate to the distribution will be  
346 tabulated for the following characteristics:

- 347 • Age
- 348 • Diabetes duration
- 349 • HbA1c at screening
- 350 • Sex
- 351 • Race/ethnicity
- 352 • Highest level of education
- 353 • Annual household income
- 354 • Type of insurance
- 355 • Body Mass Index (BMI)
- 356 • Number of hypoglycemic events that involved a seizure or loss of consciousness in the 12  
357 months prior to screening
- 358 • Number of DKA events in the 12 months prior to screening
- 359 • Daily SMBG Checks based on device downloads
- 360 • Length of Control IQ use
- 361 • Type of insulin used with control IQ prior to treatment period
- 362 • Number of non-insulin glucose lowering medications

## 363 **10 Additional Analyses**

364 Summary statistics appropriate to the distribution will be tabulated for the following outcomes  
365 during the treatment period:

### 366 **10.1 Device Issues**

- 367 • Total number of device issues, overall and by issue type
- 368 • Number of occlusion alarms which prompted an infusion set change.

### 369 **10.2 Infusion Site Reactions**

370 The following metrics will be tabulated separately for the lead-in and treatment periods.

- 371 • Number of infusion site reactions (number of events and number of participants with  $\geq 1$   
372 event).
- 373 • Number of infusion site reactions resulting in an adverse event.
- 374 • Number of infusion site reactions resulting in study discontinuation.
- 375 • Number of infusion site reactions per participant
- 376 • Number of infusion site reactions per study week
- 377 • Total number of each type of reaction (erythema, induration, site pain, pruritis, edema)  
378 overall and by reaction severity (mild/moderate or severe). The total number of events  
379 and number of participants with  $\geq 1$  event will be tabulated.

TL1 SAP V4.0 08-22-23

380 The following metrics will be tabulated in the treatment period and tabulations will be stratified  
381 by reaction type (erythema, induration, site pain, pruritis, edema). Tabulations will further be  
382 stratified by pediatric and adult participants and by reaction severity (mild/moderate or severe).

- 383 • Duration of infusion site reaction
- 384 • Timing of reaction relative to Lyumjev insulin administration
- 385 • Location of infusion site reaction

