
Protocol Overview/Synopsis
	
After consent is obtained, eligibility will be assessed. Eligible participants will enter the Lead-in Period.
 
Lead-in Period:
 
The lead-in Period will last approximately 16 days, and may begin the same day the screening visit is completed. Participants will switch from their current Control-IQ system to the study pump (Control-IQ 1.5 technology) and study sensor, and will be trained by qualified study staff on the new study devices including use of Humalog (insulin lispro injection). Study participation will require use of the Control-IQ technology with at least 85% of active closed loop over ~16 days of the lead-in period. The lead-in period data collection may be repeated if this threshold is not met.
 
A study meal challenge and exercise challenge will be performed with Humalog during the lead in period. Those day and overnight periods will be analyzed separately.
 
Treatment Period:
 
Participants will return to clinic to undergo device training with Lyumjev in the study pump. Participants will then use the study pump and the investigational insulin for ~90 days during the study period. Participants will have a phone follow up visit at 1 week and 3 weeks, a clinic follow up visit at 6 weeks, a phone follow up visit at 9 weeks, and a final clinic visit at ~13 weeks.
 
Participants will use the t.slim X2 insulin pump with Control-IQ technology turned on with the investigational insulin. It is acceptable to use manual mode when there is a loss of CGM data.
 
Weekly phone/email/text contacts will be performed as part of the comprehensive plan to monitor for adverse events, to include infusion site reactions.
 
Each participant will perform 3 meal and 3 exercise challenges during Lyumjev use.
 
An assessment of adverse events, using open ended questions to capture hyperglycemic and hypoglycemic events, and their underlying cause and relationship to the study device, study insulin or other parts of the system (such as the infusion set), will occur at all visits/contacts.
 
Study Safety Plan:
 
Participants will be given a blood glucose and ketone meter to use throughout the study, and will be trained on their use by qualified staff. BGM readings will be performed in accordance with the study safety plan and per CGM manufacturer instructions. Ketone readings will be performed per the study safety plan.
 
Site investigators may adjust insulin delivery profile settings as needed throughout the study in accordance with their clinical practice.

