### 386 **3.1.3 Training on Management of Hyperglycemia**

387 The t:slim X2 with Control-IQ system will issue a predictive hyperglycemia alert (Control-IQ High Alert)  
388 when the system has increased insulin delivery, but detects a CGM value above 200 mg/dL and does not  
389 predict the value will decrease in the next 30 minutes. During the course of the study, participants will be  
390 permitted to change the CGM high glucose threshold alert setting on their device or mobile app, but will  
391 be instructed to choose a value no greater than 300 mg/dL.

392 If the participant receives a Control-IQ High Alert, a prompt appears on the user interface to check the  
393 site for occlusion and test blood glucose.

394 If a participant's CGM reading is >300 mg/dL for more than 60 minutes or is  $\geq$ 400 mg/dL at any point,  
395 the participant will be instructed to take the following steps:

- 396 • Perform a blood glucose meter check.
- 397 • If the blood glucose is >300 mg/dL, check for blood ketones with the study ketone meter.
- 398 • If the ketone level is  $\geq$  0.6 mmol/L (or  $\geq$  2.5 mmol/L at any time), take correction insulin, change  
399 insulin (pump) infusion site and contact study staff. Continue to monitor their glucose and blood  
400 ketone levels until they return to normoglycemia and ketones are < 0.6 mmol/l.
- 401 • If ketones are <0.6 mmol/l, they will be advised to continue to monitor their glucose until it  
402 returns to normoglycemia and to repeat the ketone measurement in 90 minutes if necessary
- 403 • If correction insulin is administered via insulin syringe, turn Control-IQ off for four hours and  
404 until glucose level has returned to <180 mg/dL.

405 **3.1.4 Participant Reporting of Infusion Set Insertion Reactions**

406 Participants will receive a weekly contact (phone, email and/or text message) to assess any issues related  
407 to their current infusion site.

408 Participants will be instructed to take a photo at time of removal of the first 2 infusion sets and  
409 subsequently photo at the time of removal only if there is redness on skin when the infusion set is  
410 removed. Additional photos may be needed if during a virtual visit, video is not available.

411 **3.1.5 Adjustments in Insulin Pump Settings**

412 Insulin and glucose data from the Lead-in Period will be reviewed and the site investigator may adjust  

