413 insulin delivery profile settings as needed in accordance with their clinical practice.

414 **3.2 Study Visits and Phone Contacts**

415 Participants will have a phone (or video-conference) follow-up visit at 3 days, 1 week, 2 weeks, and 3  
416 weeks, a clinic follow-up visit at 6 weeks, a phone follow-up visit at 9 weeks, and a final clinic visit at 13  
417 weeks, within the windows specified below.

TARGET DAY/WEEK	VISIT OR PHONE	TARGET WINDOW (AROUND TARGET DAY/WEEK)
3 day	P	±1 day
1 week	P	±2 days
2 week	P	±2 days
3 weeks	P	±7 days
6 weeks	V	±7 days
9 weeks	P	±7 days
13 weeks	V	91-98 days

418 If necessary, visits should be completed out-of-window rather than missed. A visit is not considered  
419 missed until the next visit/phone window opens.

420 The goal will be for all participants to complete all scheduled visits. However, participants who  
421 (because of unforeseen circumstances or due to changes in contact precautions that may be needed  
422 during the evolving COVID-19 pandemic) are unable or unwilling to return for all follow-up visits  
423 will be permitted to return for key visits only as an alternative to withdrawal from the study. When a  
424 participant is placed into this status, missed visits will not be recorded as protocol deviations (since  
425 they would not be recorded as protocol deviations if the participant was dropped from the study).

426 Additional office visits may occur as needed.

427 **3.2.1 Procedures During Phone Contacts**

428 Phone contacts can be with or without video. Phone contacts will include the following:

- 429 • Assessment of device issues that have occurred
- 430 • Assessment of adverse events (such as hyperglycemia, hypoglycemia, and infusion set reactions)  
431 using open ended questions, and their underlying cause and relationship to the study device, study  
432 insulin or other parts of the system (such as the infusion set).

- 433       • Completion of a detailed case report form with respect to any infusion site reactions that have  
434       occurred.

435 For the first three contacts (3 day, 1 week, 2 week), if a video virtual visit can be done, visual inspection  
436 will be performed of the current and most recent infusion set insertion site. If video is not possible, then  
437 the participant will be requested to take a photo of the current and most recent infusion set insertion sites.

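### Infusion site reactions are tabulated for both Humalog lead-in and Lyumjev treatment, but weekly contacts, photos and early inspections are specified only for treatment, so recorded mild and moderate reactions lean upward on Lyumjev

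*SAP*

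**What the plan says.** **Tabulation.** SAP 10.2: "The following metrics will be tabulated separately for the lead-in and treatment periods". The list covers numbers of reactions, participants with at least one, reactions that became adverse events or led to discontinuation, reactions per participant, "Number of infusion site reactions per study week", and counts by type and severity. Protocol 8.10 includes the number and type of reactions among data tabulated at baseline and over 13 weeks. SAP 12 sends the 10.2 tabulations to the Trial Level Safety Review, which under Protocol 2.1 precedes enrollment of the 6-13 year olds.

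**Collection during treatment.** Protocol 3.1.4, in the Treatment Period chapter under the Lyumjev training visit, states: "Participants will receive a weekly contact (phone, email and/or text message) to assess any issues related" to the current infusion site. It continues: "Participants will be instructed to take a photo at time of removal of the first 2 infusion sets and" after that only where the skin is red. The synopsis has the weekly contacts under its Treatment Period heading: "Weekly phone/email/text contacts will be performed as part of the comprehensive plan to monitor for adverse events, to include infusion site reactions". Protocol 3.2.1 adds: "For the first three contacts (3 day, 1 week, 2 week), if a video virtual visit can be done, visual inspection" of the current and most recent sites, with a photo requested where video is not possible.

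**Collection during lead-in.** Protocol 2.5: "The lead-in period will last at least 16 days and no more than 21 days". Neither 2.5 nor the visit schedule gives a site-directed contact between the Humalog and Lyumjev training visits. The schedule marks an adverse event assessment at the Lyumjev training visit but not the physical exam. Footnote a nevertheless says "A qualified medical professional must perform a medical assessment at each office visit", and includes the skin around infusion sites in that assessment.

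**Recording.** Under Protocol 6.2.5 the reaction form for mild and moderate reactions is completed at scheduled visits and phone contacts, or in response to the weekly contact. Under 6.2.2 only severe or treated skin reactions are reportable adverse events.

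**The concern.** Two columns side by side, one row of them scaled per week, invite a reader to compare Humalog with Lyumjev. Scaling per week corrects for the length of the periods. It does not correct for how often anyone asked or looked. Since form completion is tied to contacts, a period with fewer contacts yields fewer forms, and the adverse event system does not recover untreated mild and moderate reactions.

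Protocol 1.3.1.2 names reactions to the new insulin as a possible risk, and 1.3.1.8 promises careful monitoring. In a single-arm trial the lead-in is the only period in which the same participants use another insulin under the protocol. The unequal search can do harm in two ways: an artefact may be read as a Lyumjev signal, or a real excess may be dismissed as an artefact.

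**Working it through.** The plan gives no rate, power or precision for this table, so there is no figure to reproduce. The check has four steps.

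**1. Density of scheduled site-directed assessments.** Lead-in: 1 closing visit in 16 to 21 days, so 7/16 = 0.44 to 7/21 = 0.33 per week. Treatment: Protocol 3.2 schedules 7 contacts or visits (day 3; weeks 1, 2, 3, 6, 9 and 13), and 3.1.4 adds a weekly contact.
- If the weekly contacts coincide with the scheduled ones: 13 + the day-3 contact = 14, and 14/13 = 1.08 per week.
- If all are separate: 7 + 13 = 20, and 20/13 = 1.54 per week.

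The ratio of treatment to lead-in runs from 1.08/0.44 = 2.5 to 1.54/0.33 = 4.6. The contacts around the challenges (Protocol 5.1) occur in both periods. They are not counted because no site check is specified for them.

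**2. What this could do to the rate ratio.** Assume equal true weekly rates, and that a mild reaction is recorded only if an assessment falls within *w* days of it. Then capture = min(1, *w*/interval), with an interval of 16 or 21 days in lead-in and 7 days in treatment. The recall window *w* is an assumption.

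| *w* (days) | Lead-in capture, 16 d | Ratio | Lead-in capture, 21 d | Ratio |
|---|---|---|---|---|
| 7 | 7/16 = 0.44 | 2.3 | 7/21 = 0.33 | 3.0 |
| 10 | 10/16 = 0.625 | 1.6 | 10/21 = 0.48 | 2.1 |
| 14 | 14/16 = 0.875 | 1.1 | 14/21 = 0.67 | 1.5 |
| 16 | 1.00 | 1.0 | 16/21 = 0.76 | 1.3 |
| 21 | 1.00 | 1.0 | 1.00 | 1.0 |

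Treatment capture is 1.00 in every row shown. For *w* below 7 the ratio stays at 16/7 = 2.3 or 21/7 = 3.0. The model leaves out the day-3 contact and the photos, which could raise the ratio. It also leaves out spontaneous reports, which would pull it toward 1.0.

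**3. Rows not scaled for time.** Participants with at least one reaction differ through exposure alone. At an assumed true rate of 0.05 per week in both periods, 1 - exp(-0.05 × 16/7) = 10.8% in a 16-day lead-in, against 1 - exp(-0.05 × 13) = 47.8% in 13 weeks.

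**4. Would counting only in-person findings per week cure it?** Treatment has clinic visits at weeks 6 and 13: 2/13 = 0.15 per week, against 0.33 to 0.44 in lead-in. In-person checks would then be 0.33/0.15 = 2.2 to 0.44/0.15 = 2.8 times denser in lead-in (from unrounded rates), and the bias would reverse. The denominator has to be visits, not weeks.

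**The case against.** The strongest reply is that no contrast is planned. SAP 10.2 tabulates, with no difference, test or decision rule. Where the SAP wants a Humalog-Lyumjev comparison it says so, as in 10.5, where set-change frequency is compared with a mixed model. Mild and moderate reactions enter none of the SAP section 5 safety endpoints unless treated. SAP 10.2 also has rows that depend less on solicitation: reactions that became adverse events, reactions that led to discontinuation, and the split by severity. Closer surveillance of the new insulin errs toward overstating its reactions.

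Most of this stands. A reader might infer that the plan sets up a biased formal test, but the documents contain none. A reader might also infer that nobody examines the skin during lead-in. Footnote a requires a check at the closing visit, so the unmarked schedule cell is an inconsistency and not proof of omission. Nor do the documents support a fixed inflation factor or the claim that any recorded excess would be an artefact, since every ratio above rests on an assumed recall window.

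The reply does not remove the unequal search behind the mild and moderate counts. The per-week row still invites comparison, nothing in the SAP warns of the difference, and the erring-high argument does not cover a true excess being explained away.

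**Conclusion.** The point holds for mild and moderate reactions. More frequent solicitation on Lyumjev can raise their recorded frequency relative to Humalog but cannot lower it, so the direction follows from the documents. The size does not. Under the recall model it runs from no distortion, if recall spans the whole lead-in, to an apparent ratio of about 3.0 with a 21-day lead-in and recall of 7 days or less. Severe or treated reactions are less affected because they are reportable in their own right. The table is descriptive, so the consequence is a misleading presentation, including in the safety review that draws on it. No trial conclusion formally depends on it.

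**What to change.** **In the protocol.** In 2.5, apply the 3.1.4 weekly infusion-site contact and removal photos to the lead-in. Mark the skin exam at the Lyumjev training visit in the schedule so that it agrees with footnote a. Cost: about two messages per participant and slightly more data entry.

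**For data already collected without this** (the SAP version 4.0 history records follow-up as complete), change SAP 10.2 as follows:
- Keep the lead-in column, but limit any between-period comparison to ascertainment common to both: reactions present on in-person skin examination, per visit (Lyumjev training visit against the 6- and 13-week visits), and severe or treated reactions per person-time.
- Report reactions found by weekly contact, photo or video for treatment only.
- Add a table footnote stating the difference in ascertainment.
- If the form does not record how a reaction was detected, say so and draw no between-period comparison of mild and moderate reactions.

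The cost here is SAP wording and a less complete, less precise comparison. With 160 participants, a 16-day lead-in gives 160 × 16/365.25 = 7.0 person-years, against 160 × 91/365.25 = 39.9 in treatment, so severe or treated reactions will be compared with little precision.
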